4.8 Safety Analysis

Safety analyses will be conducted on treated subjects by enrollment group and overall, unless otherwise noted. Safety outcome measures include: AEs, laboratory assessments including liver toxicity, vital signs, physical measurements, electrocardiograms (ECGs), and S-STS.

Select safety parameters will be summarized as continuous parameters at baseline and each scheduled visit over time during the on-treatment and follow-up safety analysis periods. Post-

baseline measurements will be first slotted into analysis visit windows in the post-enrollment and follow-up analysis periods (see Section 5.4). Post-baseline measurements will then be slotted into safety analysis periods (on-treatment and follow-up). If a subject has multiple values in an analysis visit window during a safety analysis period, then the non-missing value closest to the target date for the visit will be used; in the case of a tie, the latest value collected (from the central laboratory, if applicable) will be used. In these tables, the latest non-missing value collected (from the central laboratory, if applicable) among those at analysis visits Weeks 2 to 56 that fall in the follow-up safety analysis period will be summarized under the “Follow-up EOT” visit. See Sections 4.5, 5.4 and 5.5 for definitions of baseline, analysis periods, and analysis visit windows, respectively.

By-subject listings of safety data are described in subsections. In addition, a by-subject listing of procedures will be provided for screened subjects.

A by-subject listing of safety narrative subject identifiers will be provided for screened subjects with select events, as described in the BHV3000 Core SAP. The listing will flag subjects with select events.

4.8.1 *Extent of Exposure*

Study medication is rimegepant 75 mg tablet. This is dispensed in bottles containing 30 tablets of 75 mg rimegepant at the baseline visit and at study visits as needed; subjects should finish a bottle of study medication (containing 30 tablets of drug) prior to starting a new bottle.

Subjects are instructed to provide study drug taken status (yes, no) and number of tablets in their eDiaries every day after they are determined to be eligible to take study drug. If a subject did not report any study drug data in the eDiary on a given day, then it is assumed that the subject did not take study drug that day. Study drug records will come from the treatment epoch.

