Drug accountability is provided by the site on the Drug Accountability CRF.

A by-subject listing will present eDiary exposure (i.e., number of tablets taken) and drug accountability for treated subjects.

Another by-subject listing will present eDiary exposure (i.e., total number of tablets taken) in 4-week intervals during the LTT for treated subjects. This will also display cumulative rimegepant exposure from both sources (i.e., eDiary and drug accountability), and flag subjects with ≥ 10 cumulative tablet difference between the 2 sources.

Another by-subject listing will present batch numbers for treated subjects.

eDiary Exposure

eDiary exposure will be summarized descriptively for treated subjects by enrollment group and overall, and will include the following parameters:

- Time in the OP (weeks), defined as (OP end date – OP start date + 1)/7
- Time from enrollment to last contact (weeks), defined as (last contact date – IWRS enrollment date + 1)/7
- Time in the LTT period (weeks), derived as (LT_T end date – LT_T start date + 1)/7
- Time on rimegepant (weeks), derived as (study drug end dose date – study drug first dose date + 1)/7.*
- Cumulative rimegepant exposure (tablets), derived by summing number of tablets across records with complete dates for subjects who reported taking study medication during the treatment epoch in the eDiary.*
- Average rimegepant exposure (tablets per 4 weeks), derived as 4*cumulative rimegepant exposure/time in the LTT period.*
- Number and percentage of subjects in the average rimegepant exposure (tablets per 4 weeks) categories defined in Section 4.2.6, and also in the following categories:
 - ≥ 12.6 ($\geq 90\%$ compliant with EOD dosing)
 - ≥ 11.2 ($\geq 80\%$ compliant with EOD dosing)
- Number and percentage of subjects who took more than 1 tablet per day on any day. This could be from the same bottle or different bottles due to an unscheduled visit.
- Exposure over time, as defined by the number and percentage of subjects who took
 - ≥ 8 tablets per 4 weeks for 4, 8, 12, 16, 20, ≥ 24 , ≥ 12 , and ≥ 4 weeks. These categories correspond respectively to 1, 2, 3, 4, 5, ≥ 6 , and ≥ 3 4-week intervals that are not necessarily consecutive (see below)
 - ≥ 12 tablets per 4 weeks for 4, 8, 12, 16, 20, ≥ 24 , ≥ 12 , and ≥ 4 weeks
 - ≥ 13 tablets per 4 weeks for 4, 8, 12, 16, 20, ≥ 24 , ≥ 12 , and ≥ 4 weeks

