- Hepatic-related AEs leading to study drug discontinuation (secondary safety endpoint, see Section 4.6.2).

4.8.3 **Laboratory Tests**

Clinical safety laboratory testing will be performed at early termination and the following visits: Screening; Baseline; Weeks 4, 24, and 52 for the 52-week PRN (2-8) and (9-14) dosing groups; Weeks 4 and 12 for the 12-week EOD+PRN and PRN (2-8) dosing groups. Urinalysis will be collected at early termination and the following visits: Baseline; Week 52 for the 52-week PRN (2-8) and (9-14) dosing groups; Week 12 for the 12-week EOD+PRN and PRN (2-8) dosing groups. Lipids (cholesterol, HDL cholesterol, LDL cholesterol, triglycerides) will be collected at early termination and the following visits: Baseline; Weeks 24 and 52 for the 52-week PRN (2-8) and (9-14) dosing groups; Week 12 for the 12-week EOD+PRN and PRN (2-8) dosing groups. LFTs (ALT, AST, ALP, TBL, direct bilirubin) will be collected routinely at Screening, Baseline, all visits during the treatment period, early termination, and Follow-up Week 2 for all enrollment groups.

Clinically significant laboratory abnormalities will be identified as grade 3 to 4 laboratory test results. Refer to the BHV3000 Core SAP for laboratory tests of clinical interest and toxicity grading. Laboratory test groups of clinical interest will include hematology, serum chemistry, and urinalysis.

LDL cholesterol and triglycerides will be analyzed as separate laboratory test parameters according to 8-hour fasting status: fasting \geq 8 hours; not fasting \geq 8 hours; overall. Refer to the BHV3000 Core SAP for additional details.

Tables, listings, and figures (TLFs) will be provided to show data in both Systeme Internationale (SI) and United States (US) unit systems, if applicable.

Tables will present results by treatment group and overall, and laboratory tests alphabetically within laboratory test group, as applicable. In analyses of the worst abnormality or category in a safety analysis period, subjects must have a non-missing measurement in the safety analysis

period to be included for a given parameter. In shift from baseline analyses, subjects must have a non-missing measurement at baseline and in the safety analysis period to be included for a given parameter.

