5.3 Derived Dates

Derived dates for defining analysis periods are defined as follows:

- OP start date/time: Earliest complete date during the screening epoch in the eDiary.
- OP end date/time: Latest complete date during the screening epoch in the eDiary.
- LTT start date/time: Earliest complete date during the treatment epoch in the eDiary.
- LTT end date/time: Latest complete date during the treatment epoch in the eDiary.
- Study drug first dose date/time: Earliest complete date where subjects indicated that they took medication during the treatment epoch in the eDiary.
- Study drug end dose date/time: Latest complete date where subjects indicated that they took medication during the treatment epoch in the eDiary.
- Study drug last dose date/time: Study drug end dose date derived only for subjects who have non-missing completion status on the Study Exit Status CRF. Thus, in an interim analysis, all post-treatment data will be included for a subject who is still on study. At the last database lock, the last dose date will be equal to the end dose date for treated subjects.
- EOT visit date: Maximum of the following: (1) LTT end date/time; (2) latest complete visit date excluding folder name “follow-up safety visit” on the Visit Date CRF. This is derived only for subjects who have non-missing completion status on the Study Exit Status CRF.

- Last contact date: (1) Complete death date, if it exists; (2) otherwise, the maximum complete date of the following: AE start/stop; ECG; eDiary; enrollment; informed consent; laboratory collection; non-study medication start/stop; physical measurement; procedure; rating scale; questionnaire; screening; study completion/discontinuation; vital sign; visit.

No imputations are performed on these derived dates. Complete dates are those with valid, non-missing day, month, and year.

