5.4 Analysis Periods

Analysis periods are defined as follows:

- Observational Period (OP): measurement date/time on or after the OP start date/time through the OP end date/time. This period is used to assess the number of migraine days per 4 weeks during the OP.
- Pre-treatment: measurement date/time on or before the study drug first dose date/time. This period is used to derive baseline values, and to assess safety and outcomes research endpoints.
- Post-enrollment: measurement date/time after the IWRS enrollment date/time through the EOT visit date + 7 days. This period is used to derive analysis visit windows for slotting observations.
- Follow-up: measurement date after the EOT visit date + 7 days. This period is used to slot observations.
- Long-term treatment (LTT): measurement date/time on or after the LTT start date/time through the LTT end date/time. This period is used to assess the number of migraine days per 4 weeks and number of tablets taken during LTT.
- On-treatment safety: measurement date/time after the study drug first dose date/time through the study drug last dose date + 7 days. Note that AEs with imputed start date equal to the study drug first dose date are part of this period (refer to the BHV3000 Core SAP for AE start date imputation). This period is used to assess safety endpoints on treatment.
- Follow-up safety: measurement date after the study drug last dose date + 7 days. This period is used to assess safety endpoints during follow-up.

See Section 5.3 for derived dates for determining analysis periods. If measurement time is missing or not collected, then the measurement date will be compared to the derived date.

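### Closing on-treatment safety at the last tablet + 7 days moves some as-needed completers' end-of-treatment laboratory and ECG results out of the on-treatment worst-grade and shift tables; a paired column would show the effect

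*SAP*

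**What the plan says.** SAP 5.4 sets the on-treatment safety period as "measurement date/time after the study drug first dose date/time through the study drug last dose date + 7 days"; anything later belongs to the follow-up safety period. SAP 5.3 takes the dose dates from the eDiary. At final lock the last dose is the latest treatment-epoch day on which a tablet was reported, and under SAP 4.8.1 a day without dosing data counts as a day without a tablet. There is no exception for as-needed dosing. While a subject's exit status is still missing, the cut-off does not apply: "Thus, in an interim analysis, all post-treatment data will be included for a subject who is still on study".

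The SAP foresees results that fall beyond the cut-off. SAP 4.8 places the latest value "among those at analysis visits Weeks 2 to 56 that fall in the follow-up safety analysis period" in a Follow-up EOT row of the by-visit tables. SAP 4.8.3 adds a follow-up worst-grade table by enrollment group, SAP 4.6.3.1 a follow-up liver-test table, and SAP 4.8.5 follow-up QTc abnormalities.

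The schedule is sparse: "Clinical safety laboratory testing will be performed at early termination and the following visits: Screening; Baseline; Weeks 4, 24, and 52" for the 52-week groups, and "Weeks 4 and 12 for the 12-week EOD+PRN and PRN (2-8) dosing groups". ECGs follow the same treatment-phase weeks (SAP 4.8.5). For urinalysis: "Urinalysis will be collected at early termination and the following visits: Baseline; Week 52 for the 52-week PRN (2-8) and (9-14) dosing groups".

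The worst-grade laboratory table, its subgroup version, the three laboratory shift tables (low/normal/high, liver tests against ULN, toxicity grade) and the ECG-interpretation shift table all use on-treatment values (SAP 4.8.3, 4.8.5).

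**The concern.** In the 2-8 and 9-14 groups, tablets are taken only for a migraine, so a tablet-free week is ordinary use within the protocol. In mid-study such a week is on-treatment because a later tablet follows. At the end of the treatment phase no later tablet follows, and the EOT result moves to follow-up. Time in the same tail still counts in the exposure measure that defines the subgroups: "Average rimegepant exposure (tablets per 4 weeks), derived as 4*cumulative rimegepant exposure/time in the LTT period".

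Three gaps remain in the tables:

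- The follow-up worst-grade table is not produced by exposure subgroup.
- No laboratory or ECG-interpretation shift table covers follow-up.
- No table combines grade 3-4 results across periods, although SAP 4.8.2 does combine periods for adverse events leading to discontinuation.

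At stake is a component of the primary endpoint. An affected 52-week completer loses one of three scheduled post-baseline chemistry/haematology and ECG assessments, and the only scheduled post-baseline urinalysis.

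**Working it through.** The documents state no figure for how many results this affects, so there is none to reproduce. The boundary follows from the text. The size needs assumptions.

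**Boundary.** Let D be the collection date of the EOT sample or ECG. If the last tablet was on D-7, then D = last dose + 7 and the result is on-treatment. If it was on D-8 or earlier, the result is follow-up. Affected completers are exactly those with no tablet on the eight dates D-7 to D. A subject adhering to every-other-day dosing is never affected.

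**Share affected (assumed rate of r tablets per 28 days).**

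| r | Independent days, (1 - r/28)^8 | Poisson, exp(-8r/28) | Clustered (negative binomial, k = 1), 1/(1 + 8r/28) |
|---|---|---|---|
| 2 | 55.3% | 56.5% | 63.6% |
| 4 | 29.1% | 31.9% | 46.7% |
| 8 | 6.8% | 10.2% | 30.4% |
| 14 | 0.4% | 1.8% | 20.0% |

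**By group.** These use entry attack frequency as the tablet rate per 30 days, with whole-number rates equally weighted:

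- 2-8 group: 27.5% (independent), 30.3% (Poisson), 45.3% (clustered).
- 2-8 group at 1.5 times that rate, because mild attacks may also be treated: 15.4%, 18.3%, 36.0%.
- 9-14 group: 2.6%, 5.2%, 24.9%.

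The range of about 15% to 45% for the 2-8 group runs from independent days at 1.5 times the entry rate to clustered use at the entry rate.

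**Effect on the percentage with any grade 3-4 result.** Assume three draws with the same independent risk q each. A subject with all three draws has probability 1 - (1 - q)^3, and an affected subject 1 - (1 - q)^2. At q = 0.5% these are 1.493% and 0.998%, so the relative loss is share x (1.493 - 0.998)/1.493 = share x 0.332. With independent days this is 18.3% at 2 tablets, 9.7% at 4, 2.3% at 8 and 0.1% at 14. At 2 tablets the table would read 1.22% instead of 1.49%; at 8 tablets, 1.46%.

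**Moved results per test, 2-8 group.** With independent days at entry frequency, about 331 EOT draws move if all 1200 complete, and 198 if 60% do. At a risk of 0.1% to 1% per draw this gives 331 x 0.001 to 331 x 0.01 = 0.3 to 3.3, or 0.2 to 2.0. Clustered use with all completing (544 draws) gives 0.5 to 5.4.

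**Liver tests.** The 52-week schedule has 14 treatment-phase draws (Weeks 2 and 4, then every 4 weeks from Week 8 to Week 52). Losing the EOT draw leaves 13.

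**Direction.** If the subject has another on-treatment draw for the test, the denominator is unchanged and the numerator can only fall. For urinalysis in the 52-week groups there is normally no other draw. SAP 4.8.3 requires a non-missing value in the period, so the subject leaves the denominator and the percentage can move either way.

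**The case against.** The strongest reply is that the rule is deliberate and coherent. Time on rimegepant, patient-years, time to rimegepant discontinuation (all SAP 4.8.1) and the exposure-adjusted reference dates (SAP 4.8.2) all rest on the last tablet, and the safety window follows that convention. Version 2.0 changed the on-treatment definition and added the follow-up period and its laboratory tables together. An affected subject is a follow-up subject by definition (SAP 3), so the result is tabulated and listed. Clinically significant laboratory results are also recorded as adverse events (Protocol 8.2.2). All of this stands, and what remains is mainly table placement.

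The size model is also open to attack. It gives a draw at least eight days after the last tablet the same risk as one nearer dosing. It ignores persistence, so an abnormality already counted at Week 24 is treated as if it could be lost. The relative losses assume that all three draws were taken. These points stand too, and they make the percentages illustrative only.

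A reader might infer more than the documents support:

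- *That results are dropped.* They are reclassified and remain visible.
- *That the SAP breaches the protocol.* Protocol 9.3.1 refers to on-treatment laboratory data without defining the term.
- *That an exposure signal is hidden.* Low-exposure strata would lose more results, which exaggerates a gradient rather than masking it. The strata also differ by design in number of draws and length of follow-up.
- *That monitoring stops for the last 28 weeks.* No 52-week completer has scheduled chemistry between Weeks 24 and 52; one draw moves.

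**Conclusion.** The point holds as a matter of tabulation, at low severity. The boundary is certain from SAP 5.3 and 5.4, and so is the absence of affected results from the listed on-treatment tables. Where other on-treatment draws exist, the percentage with any grade 3-4 result can only be understated relative to a window that includes the EOT visit, and the expected loss is larger in low-exposure strata. For urinalysis the direction is open.

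The size is unknown: every share above rests on an assumed tablet rate and pattern of use, and every count on an assumed risk per draw. On those assumptions the affected share of the 2-8 group is not negligible, but few grade 3-4 results per test would move. Liver-test and adverse-event effects are small, and the study's validity is not in question.

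**What to change.** For the worst-grade laboratory tables (including exposure subgroups) and the laboratory and ECG-interpretation shift tables, add a paired column that includes results through the later of last dose + 7 days and the scheduled EOT or early-termination visit. Keep the current window as the stated analysis.

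Define the extension by the scheduled visit. The derived date in SAP 5.3 is unsuitable without a guard: "EOT visit date: Maximum of the following: (1) LTT end date/time; (2) latest complete visit date excluding folder name" of the follow-up safety visit. A late unscheduled visit would therefore lengthen on-treatment time.

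Leave the adverse-event tables, the rule linking liver tests to concurrent adverse events (SAP 4.6.3.2) and the exposure-adjusted rules on the current window. Footnote that an adverse event reported for an EOT laboratory result may be classed as follow-up while the result itself is counted in the added column.

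The cost is SAP wording, one date flag and the extra columns, with no protocol amendment and no new data. The downside is that some off-drug time in subjects who stopped dosing early enters the added column; the paired display makes that visible.

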5.5 Analysis Visit Windows

Refer to Protocol Section 4.3 for the schedule of assessments.

Study days are calculated from enrollment as follows:

- Measurement date – IWRS enrollment date + 1, if measurement date \geq IWRS enrollment date
- Measurement date – IWRS enrollment date, if measurement date $<$ IWRS enrollment date

Follow-up days are calculated from the EOT visit as follows:

- Measurement date – EOT visit date + 1, if measurement date \geq EOT visit date
- Measurement date – EOT visit date, if measurement date $<$ EOT visit date

Evaluation intervals are based on study days derived in the post-enrollment analysis and follow-up analysis periods (see Section 5.4). [Table 5](#) and [Table 6](#) have analysis visit windows for the PRN and EOD+PRN dosing groups, respectively.

Table 5: Analysis Visit Windows: 52-Week PRN (2-8) and (9-14) Dosing Groups

Visit	Analysis-Specified Interval for PoM, SM, MSQoL, MIDAS, and CGI-C	Analysis-Specified Interval for Other Endpoints	Target Day
Screening Period			
Screening	≤ -1	≤ -1	
Baseline	1	1	1
Post-Enrollment Period			
Week 2		2 to 21	14
Week 4		22 to 42	28
Week 8		43 to 70	56
Week 12	43 to 126	71 to 98	84
Week 16		99 to 126	112
Week 20		127 to 154	140
Week 24	127 to 210	155 to 182	168
Week 28		183 to 210	196
Week 32		211 to 238	224
Week 36	211 to 308	239 to 266	252
Week 40		267 to 294	280
Week 44		295 to 322	308
Week 48		323 to 350	336
Week 52	≥ 309	351 to 378	364
Week 56		≥ 379	392
Follow-up			
Follow-up Week 2		8 to 21	14
Follow-up Week 4		≥ 22	28

Study days are used for screening and post-enrollment; follow-up days are used for follow-up.

Table 6: Analysis Visit Windows: 12-Week EOD+PRN and PRN (2-8) Dosing Groups

Visit	Analysis-Specified Interval for PoM, SM, MSQoL, MIDAS, and CGI-C	Analysis-Specified Interval for Other Endpoints	Target Day
Screening Period			
Screening	≤ -1	≤ -1	
Baseline	1	1	1
Post-Enrollment Period			
Week 2		2 to 21	14
Week 4		22 to 42	28
Week 8		43 to 70	56
Week 12	≥ 43	71 to 98	84
Week 16		99 to 126	112
Follow-up			
Follow-up Week 2		8 to 21	14
Follow-up Week 4		≥ 22	28

Study days are used for screening and post-enrollment; follow-up days are used for follow-up.

LTT study days are used in analyses of migraine days and exposure, and are calculated from LTT start as follows:

- Measurement date – LTT start date + 1, if measurement date ≥ LTT start date
- Measurement date – LTT start date, if measurement date < LTT start date.

6 CHANGES TO PLANNED ANALYSES IN THE PROTOCOL

There are no changes to planned analyses in the protocol at this time.
